1.1.2 Clinical Effects of Oral Mucositis

The severity of OM varies from superficial erythema, accompanied by soreness, to full-thickness mucosal ulcerations, necessitating parenteral narcotics for pain control (Scully et al., 2006). Among patients receiving myeloablative CT regimens or RT to the head and neck, OM is the most commonly cited bothersome adverse event (AE) associated with treatment (Rose-Ped et al., 2002).

The clinical impact of OM is profound, especially when ulceration is present. Even OM described as slight to moderate is associated with increased oral pain, weight loss, the need to modify diet, dehydration, and reduced performance status (Elting et al., 2007). Oral mucositis results in loss of critical functions, such as the ability to eat and to swallow, which can lead to dehydration, weight loss, and the need for nutritional support (e.g., gastrostomy tube placement). Furthermore, the ulcerations associated with OM are a frequent site of secondary infections and, in myelosuppressed patients, may act as portals for systemic bacterial spread (Reuscher et al., 1998). Treatment breaks prompted by patients' inability to tolerate the symptoms associated with OM compromise cancer therapy. And there is a strong association between OM and diminished quality-of-life (QOL) outcomes (Elting et al., 2008).

Besides its symptomatic toll, OM is associated with a number of negative health and economic outcomes, including increased analgesic and antibiotic use, number of febrile days, need for parenteral nutrition, prolonged length of hospital stay, and

This document contains confidential information. It is intended solely for the use of the principal investigator, co-investigators, staff, appropriate institutional review boards or ethical committees, and other required regulatory bodies.

increased resource use and associated cost. In granulocytic patients, mucositis is strongly associated with an increased risk of bacteremia and sepsis (Reuscher et al., 1998). Among patients treated for HNC, even mild OM results in more frequent hospitalization and breaks in treatment (Vera-Llonch et al., 2006).

Despite its frequency and significance, there is no approved intervention for RT-induced OM in HNC. Furthermore, currently there is a single agent approved as a treatment for OM, Kepivance[®], and its application is limited to OM associated with conditioning regimens prior to stem cell transplant for the treatment of hematologic malignancies.

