4.2.1 RADIATION THERAPY TREATMENT PLAN

Subjects will receive a continuous course of intensity-modulated radiotherapy with a minimum cumulative dose of 50 gray (Gy) and maximum dose of 72 Gy. Planned radiation treatment fields must include at least 2 at-risk sites for OM (maxillary or mandibular labial mucosa, right or left buccal mucosa, right or left ventral and/or lateral tongue, floor of oral cavity, or soft palate/tonsillar pillars) with each site receiving a total dose of \geq 50 Gy.

Radiation dose delivery will be clearly documented.

Changes in the radiation therapy plan will be allowed. However, the changes (example: dose delay, changes in the planned radiation dose or number of fractions) and the reason for the change should be clearly documented.

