The effect of treatment on the primary efficacy endpoint will be examined within subject subgroups defined by region (US vs Europe), cisplatin regimen, HPV status and baseline disease characteristics (primary cancer diagnosis for 3 subcategories: oral cavity, oropharynx and all other). Descriptive summary statistics will be used for this purpose.

The following sensitivity analyses will be performed using alternative methods for the analysis of duration of severe OM in the ITT, mITT, and PP populations:

- Repeat the primary analysis using the worst adjacent imputation strategy for gap days, replacing the days without a value with the worst value between the closest previous and following values.
- Repeat the primary analysis but using imputation for missing data. For subjects with unresolved SOM, use the median value for subjects in the same treatment group with at least that duration. For subjects without severe OM but with incomplete follow-up (i.e., discontinued before the end of the active treatment period with no short-term follow-up OM assessments), use the median duration among patients in the same treatment arm who were free of severe OM for at least that length of follow-up.
- Calculate severe OM duration as the total number of days a subject has a grade 3 or 4 mucositis from the start of CRT until the end of the short-term follow-up phase, with last observation carried forward (LOCF) imputation (so, the OM grade at a day without assessment is considered to be the same as at the closest previous valid assessment).
- Same as the above, but using the worst adjacent imputation strategy for gap days (i.e. replacing the missing value with the worst value between the closest previous and following values).
- Repeat the primary analysis but using only the period from start of CRT to the actual last day of CRT to define duration of severe OM.

Listings of individual WHO OM grades and calculated primary endpoint values will be created.

The distribution of OM severity grades at each visit will also be displayed. These summary tables will present the number and percentage of patients per OM grade at each visit, by treatment group, for the ITT, mITT, and PP populations.

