the number subjects in the treatment group. A stratified CMH test (general association statistic) will be used to compare proportions and test whether or not AG013 reduces the incidence of severe OM. Incidence will be calculated for two observation periods: (1) entire follow-up period, and (2) from the first to last day of CRT. Incidence of severe OM will also be summarized descriptively for subgroups defined by 3 factors (cisplatin regimen, region, HPV status) in the mITT population only.

Duration of ulcerative OM: The duration of ulcerative OM (WHO grade 2, 3 or 4) will be calculated in a manner similar to duration of severe OM. That is, the duration of ulcerative OM will be calculated as the number of days from the onset of ulcerative OM (first time a WHO grade 2, 3 or 4 is observed) to the day when ulcerative OM has resolved (first time WHO grade 0 or 1 is observed after last WHO grade 2, 3 or 4). An imputation scheme similar to the primary analysis will be used in the event that subjects discontinue prior to resolution of OM to grade 0 or 1. The stratified CMH test (with modified ridit scores) will be used to compare treatment groups and test whether or not AG013 reduces the duration of ulcerative OM.

Time to onset of ulcerative OM: Time to onset of ulcerative OM (WHO grade 2, 3 or 4) will be calculated and analyzed as described above for severe OM.

Incidence of ulcerative OM: Incidence of ulcerative OM (WHO grade 2, 3 or 4) will be calculated and analyzed as described above for severe OM.

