8.7.3 ANALYSIS OF OTHER SECONDARY EFFICACY ENDPOINTS

Cumulative radiation dose to development of severe oral mucositis: Total cumulative dose of radiation (in Gy units) until the date of first severe OM (WHO grade 3 or 4) will be calculated for each subject and summarized by treatment group using descriptive statistics in the mITT population. Similarly, the cumulative radiation dose up to the first observed ulcerative oral mucositis (WHO grades 2-4) will be tabulated. If a subject does not experience severe OM during the study, the full cumulative radiation dose will be used. The difference between treatment groups will be evaluated using the stratified CMH test (with modified ridit scores). This test will determine whether the AG013 group achieved a higher cumulative radiation dose before onset of severe OM, compared to the placebo group.

Patient-reported pain: The average of patient-reported MTS scores, graded on a scale from 0 (no soreness) to 4 (extreme soreness), will be summarized by treatment group during each study week as well as for the last 7 days of treatment in the mITT population.

The difference between treatment groups will be evaluated using the stratified CMH test (with modified ridit scores) to determine whether or not AG013 reduces pain.

Other Diary Outcomes: For other diary items: overall health, limited in swallowing, drinking, eating, talking and sleeping, overall soreness and diarrhea descriptive statistics will be produced for each treatment and by study week as well as for the last 7 days of treatment in the mITT population. However, no significance tests will be performed.

Analgesic use: Use of analgesics (parenteral, oral, or transdermal) to control oral pain will be examined by displaying number and percentages of subjects in the mITT population taking:

- Topicals such as viscous lidocaine
- OTC analgesics such as acetaminophen or ibuprofen
- PO opioids such as Vicodin or Percocet
- Parenteral opioids such as morphine or Fentanyl

Also, PO and Parenteral opioids will be combined to form a category for all opioids. Pvalues for all opioids and parenteral opioids will computed using the stratified CMH test (with modified ridit scores).

All the patient-level secondary endpoints will be listed together with the primary endpoint. Listings of radiation therapy data, OMDQ, and analgesics will be created as well.

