8.7.4 EXPLORATORY EFFICACY ENDPOINTS

Exploratory efficacy analyses will be conducted for the mITT population only. The effects of AG013 will be explored on the basis of the following:

Descriptive statistics will be presented for the incidence of severe OM (WHO grades 3 or 4) within subgroups receiving each of the following cumulative radiation doses: <=30 Gy, >30 and <= 40 Gy, >40 and <= 50 Gy, >50 and <= 60 Gy, and > 70 Gy. As with the secondary endpoint analysis, incidence will be defined as the proportion of subjects in each subgroup having at least one grade 3 or 4 OM assessment.

The distribution of OM severity grades at each visit will be provided for CTC and RTOG rating scales. These summary tables will display the number and percentage of patients per OM grade at each visit, by treatment group, for the mITT population.

For each subject, oral mucositis severity scores (WHO grades 0-4) at each time point will be used to calculate AUC using the trapezoidal rule. Average severity-by-time curves will

be generated and plotted for each treatment group, and compared using the Wilcoxon rank-sum test. Descriptive statistics for AUC values will be presented.

Incidence, duration and time to onset of grades 3 and 4 and grades 2, 3, and 4 OM as per NCI CTCAE and RTOG criteria will be analyzed separately, using the same methodology as described for the primary and secondary endpoints. Listings of NCI CTCAE and RTOG grades will be prepared, as well as listings of the calculated endpoints.

Frequency and duration of RT interruptions: The number of subjects in each treatment group with an unplanned break in RT during the 7- to 9-week regimen will be tabulated. Subjects with an interval of 5 days or more without an administration of RT, or who discontinue RT prior to completing the planned RT regimen, will be considered to have an unplanned break in RT. The duration of unplanned RT interruptions (in days) will also be summarized by treatment group using descriptive statistics. For subjects who prematurely discontinue RT, the time from the last dose of RT to the prescribed end date of the regimen will be used in the calculation.

All the RT data will be listed. Calculated values for the above listed endpoints will be listed separately.

The number of unplanned office visits, ER visits, hospitalizations, and non-prophylactic gastrostomy tube placements (US sites only) in each treatment group will be tabulated.

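### The CRT-only sensitivity analysis of severe OM duration stops the clock on the actual last day of CRT, a date that OM itself can move; the planned last day would avoid this

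*SAP*

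**What the plan says.** The primary analysis in SAP 8.7.1 uses every OM grade through short-term follow-up. If a subject dies or withdraws with severe OM unresolved, severe OM is assumed to last to Day 91. Stopping CRT while staying in the study does not trigger that rule.

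Five sensitivity analyses follow. The last repeats the primary analysis "using only the period from start of CRT to the actual last day of CRT to define duration of severe OM". No rule covers a subject whose CRT ends early. The SAP does not say whether the Day 91 imputation is capped at this window, or whether the last day of CRT means the last radiation fraction or the last cisplatin dose.

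The documents connect that date to OM:

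- Protocol 1.1.2 says that treatment breaks arising from patients' "inability to tolerate the symptoms associated with OM compromise cancer therapy", and that "even mild OM results in more frequent hospitalization and breaks in treatment".
- SAP 4.2.1: "Changes in the radiation therapy plan will be allowed".
- SAP 8.7.4 counts subjects who "discontinue RT prior to completing the planned RT regimen" among those with an unplanned break, and measures the gap to the prescribed end date of the regimen.

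The protocol was set up differently. Section 10.5 ends its imputation 2 weeks after the last planned dose of CRT, and its active-phase sensitivity window runs to 14 days after CRT is completed. SAP Section 9 does not list the shorter window as a deviation.

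**The concern.** The window length is itself an outcome. Two subjects with the same OM course get different scores if one is taken off CRT because of it. The one whose OM was bad enough to end treatment is recorded as having had less of it. A delay works the other way, because a later last day adds countable days.

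SAP 8.3 says the sensitivity analyses are there to show that the primary result is robust. An analysis whose result moves with the rate of early CRT stops cannot be read that way. If it agrees with the primary analysis, part of the agreement may come from stopping patterns. If it disagrees, the disagreement may be spurious.

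**Working it through.** **The plan's own figure.** The plan gives no number for this analysis. The nearest is the power of the primary comparison (80 per group, 5-day difference, SD 10.8). The standardised difference is 5 / (10.8 × √(2/80)) = 2.93, and the normal approximation gives Φ(2.93 − 1.96) = 83% (exact t: 82.9%) against the stated approximately 80%. Nothing below depends on it.

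**One subject.** Assume 70 Gy in 2.0 Gy fractions, within the permitted 50 to 72 Gy and 2.0 to 2.2 Gy, five fractions a week. That is 35 fractions, or seven weeks, so the last falls on Day 6 × 7 + 5 = 47. Severe OM starts on Day 22 and is still present on Day 47.

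- CRT stopped on Day 29 because of OM: actual-date window 29 − 22 = 7 days.
- Same subject, planned-date window: 47 − 22 = 25 days.

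**Average effect.** Assumptions, none from the documents:

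- Severe OM onset is uniform over Days 15 to 47 and lasts to the planned end.
- A proportion s of severe cases stop CRT, uniformly 0 to 10 days after onset (or at the planned end if sooner).

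The severe OM rates of 75% (placebo) and 50% (AG013) are from SAP Section 6.

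Mean planned-window duration per severe case is 32/2 = 16 days. The mean loss per stopper is (32³ − 22³) / (3 × 10 × 64) = 22,120 / 1,920 = 11.52 days. The placebo-minus-AG013 difference in the actual-date window, with severe OM rates p and subscripts P and A for placebo and AG013, is then

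16 × (p_P − p_A) − 11.52 × (p_P s_P − p_A s_A).

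| Stop rate, AG013 v placebo | Severe OM 50% v 75% | Severe OM 75% v 75% |
|---|---|---|
| none | 4.00 | 0 |
| 5% v 5% | 3.86 | 0 |
| 10% v 10% | 3.71 | 0 |
| 5% v 15% | 2.99 | −0.86 |
| 10% v 20% | 2.85 | −0.86 |
| 10% v 30% | 1.98 | −1.73 |
| 20% v 10% | 4.29 | +0.86 |

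For example, at 5% v 15%: 4.00 − 11.52 × (0.75 × 0.15 − 0.50 × 0.05) = 4.00 − 1.01 = 2.99. A simulation of 400,000 per arm gave 3.86, 3.71, 2.85, 1.96 and 4.27 for the rows it covered. The planned-date difference stays at 4.0 throughout.

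A second simulation with different assumptions had a true difference of 3.3 days and lost about 0.2 day at 10% v 10% and up to 0.8 day at 5% v 15%. In relative terms that is 0.2/3.3 = 6% to 0.8/3.3 = 24%. The table gives 0.29/4.00 = 7% to 1.01/4.00 = 25%.

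**False rejection when the OM course is the same in both arms.** Simulations used 100 per arm, severe OM in 75% of each arm, two-sided 5% tests, and several sets of assumed onset and duration.

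| Stop rate, AG013 v placebo | Actual-date window | Planned-date window |
|---|---|---|
| 5% v 5% | 4.5 to 4.9% | about 5% |
| 5% v 10% | about 6% | about 5% |
| 5% v 15% | 8.5 to 10% | about 5% |
| 5% v 25% | 20 to 24% | about 5% |

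**The case against.** **Nothing decisive rests on it.** This is true. The primary analysis uses all grades through short-term follow-up, the other four sensitivity analyses are not cut at the end of CRT, and RT interruptions and cumulative RT are summarised, so a large imbalance in stopping would be visible. That limits the importance of the point but does not make the window suitable as a robustness check.

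**Severe OM while on CRT is a fair question.** It is, and the protocol defines its active phase from the actual end of radiation. But the SAP presents the analysis as an alternative estimate of the same duration comparison, without labelling it as conditional on remaining on CRT.

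**The null scenario is contrived.** If OM is equal in both arms and OM alone drives stopping, the stop rates should be equal, and then there is no inflation. This stands for the larger rejection rates, which need an imbalance from some other cause and are not forecasts. The loss of a true difference needs no imbalance in stop rates among severe cases: 10% in each arm already takes 4.00 to 3.71 days.

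**The planned date has a fault too.** Severe OM during radiation that runs past the planned date is not counted, and days on and off CRT are mixed. Both are real but limited costs. A date fixed at randomisation cannot be moved by the outcome in either arm.

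**Conclusion.** The point holds for one supportive analysis. The actual last day of CRT is a cut-off that OM can move, and it gives short durations to subjects whom severe OM forced off treatment. The direction is not fixed: more stopping on placebo hides benefit, and more on AG013 flatters it. The size depends wholly on stop rates, onset times and durations that the documents do not give.

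Three stronger readings are tempting but not supported:

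- **That the analysis could reverse a true result.** At 50% v 75% severe OM, the difference stays positive even at 10% v 30% stopping (1.98 days). In simulated trials the sign changed in 0.6% at 5% v 10% and 1.6% at 5% v 15%. The effect is attenuation.
- **That the CRT-only incidence window ("2) from the first to last day of CRT") has the same fault.** A subject forced off CRT by severe OM already has a grade 3 or 4 score and counts as an event. The shorter window misses only subjects who reach grade 3 after an early stop, and the SAP also reports incidence over the entire follow-up.
- **That the pain summary "during each study week as well as for the last 7 days of treatment" is cut in the same way.** The schedule footnote in both documents defines the end of treatment by the last IMP dose, and IMP continues for 14 days after CRT. For a subject who completes IMP, those seven days fall after CRT.

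**What to change.** In the fifth sensitivity bullet of SAP 8.7.1:

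- End the window on the last day of CRT planned in the RT plan at randomisation, and say how that date is defined.
- Use all OM grades recorded up to that day, whether or not CRT stopped early.
- Count a subject who withdraws with unresolved severe OM as severe to that day, in place of Day 91.
- If an on-CRT description is wanted, keep the actual-date version as a labelled descriptive summary, next to the number of early CRT stops by arm.
- Record the changed window in SAP Section 9.

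Leave the pain window and the CRT-only incidence window as they are.

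The cost is SAP wording and one date variable. SAP 8.7.4 already needs the prescribed RT end date. The grades should exist for subjects who stay in the study: assessments run twice weekly to 14 days after CRT and weekly to Day 42 after it unless OM resolves. A stop on Day 29 is therefore followed to Day 29 + 42 = 71, well past a planned Day 47. The SAP should state the two costs: severe OM days in overrunning radiation are not counted, and the window includes some days off CRT.

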8.7.2 ANALYSIS OF KEY SECONDARY EFFICACY ENDPOINTS

Statistical methods for the calculation and analysis of secondary efficacy endpoints are provided below. For each endpoint, significance testing will evaluate the superiority of AG013 compared to placebo; two-sided tests will be used to reject the null hypothesis (no difference between groups) in favor of the alternative hypothesis (there is a difference between groups). The analysis of all key secondary efficacy endpoints will be performed for the ITT, mITT and PP populations.

Note: The OM assessment period includes all OM Assessments performed, including the short-term follow-up period.

To control the experiment-wise Type 1 error rate at 5%, significance tests of the key secondary efficacy endpoints will be performed in the hierarchical order listed below. As specified in the protocol, the mITT population will be the main analysis and guide the hierarchical order of testing. To support these results, the same analyses will be repeated for ITT and PP populations. Each analysis will control for stratifications factors. All the analyses described below will be performed for the purpose of displaying summary statistics, but once the first in the sequence of tests yields a p-value that exceeds 0.05, the nominal p-value for this and subsequent endpoints in the series will be declared non-significant.

Time to onset of severe OM: Time to onset of severe OM (WHO grade 3 or 4) will be calculated as the elapsed time (in days) from the start of CRT until the date of first OM assessment grade 3 or 4. Subjects who do not experience an event by the end of the OM assessment period will be censored on the date of last OM assessment. Subjects with no post-baseline OM assessments will be censored on Day 1. Kaplan-Meier estimation methods and the stratified log-rank test will be used to compare time-to-event distributions and test whether or not AG013 delays the onset of severe OM. The log-rank test will be stratified by cisplatin regimen, HPV status and region. Below is the sample SAS code that performs the intended analysis:

```
proc lifetest
```

```
data=test;
time Time_to_Onset*censor(1);
strata CIS_GRP HPV REGION / group=TRTPN;
run;
```

Incidence of severe OM: The incidence of severe OM (WHO grade 3 or 4) will be calculated as the number of subjects with at least one OM WHO grade 3 or 4, divided by

the number subjects in the treatment group. A stratified CMH test (general association statistic) will be used to compare proportions and test whether or not AG013 reduces the incidence of severe OM. Incidence will be calculated for two observation periods: (1) entire follow-up period, and (2) from the first to last day of CRT. Incidence of severe OM will also be summarized descriptively for subgroups defined by 3 factors (cisplatin regimen, region, HPV status) in the mITT population only.

Duration of ulcerative OM: The duration of ulcerative OM (WHO grade 2, 3 or 4) will be calculated in a manner similar to duration of severe OM. That is, the duration of ulcerative OM will be calculated as the number of days from the onset of ulcerative OM (first time a WHO grade 2, 3 or 4 is observed) to the day when ulcerative OM has resolved (first time WHO grade 0 or 1 is observed after last WHO grade 2, 3 or 4). An imputation scheme similar to the primary analysis will be used in the event that subjects discontinue prior to resolution of OM to grade 0 or 1. The stratified CMH test (with modified ridit scores) will be used to compare treatment groups and test whether or not AG013 reduces the duration of ulcerative OM.

Time to onset of ulcerative OM: Time to onset of ulcerative OM (WHO grade 2, 3 or 4) will be calculated and analyzed as described above for severe OM.

Incidence of ulcerative OM: Incidence of ulcerative OM (WHO grade 2, 3 or 4) will be calculated and analyzed as described above for severe OM.

